Official Title: Optimizing Dementia Care through Collaborative Recovery Interventions

NCT: NCT02585232

1. **Principal Investigator:** [name]
2. **All co-investigators:** [name]; [name], MA; [name], MS; [name]; [name], MEd; [name], MA; [name], BA; [name], [name], BS
3. **Consultants:** [name]; [name]; [name]; [name]
4. **Sponsor of the study or funding agency (if applicable):** VA Rehabilitation Research & Development Service (Rehab R&D) (D1824-W; Application Number: 1IK2RX001824-01A1)

5. Research setting:

This is a community-based study. All in-person study procedures will occur in a convenient community-based setting of the participant's choosing (e.g., their home, a local library, a community center, TVAMC campus, etc.). Most interactions (intervention & assessment) will occur over the telephone.

6. Purpose of the study (including hypothesis to be tested):

The purpose of this randomized controlled pilot study is to examine the preliminary effectiveness, feasibility, and potential treatment moderators (e.g., behavioral symptoms and spousal relationship status) of a newly developed intervention that combines elements of the established care consultation (CC) approach with additional counseling modules (CC+C).

Our specific aims and hypotheses follow:

Aim 1: Manualize the integration of care consultation and counseling components. The study team will begin this five-year study by refining and operationalizing the CC+C intervention. The CC+C intervention is guided by a rehabilitation and recovery-based conceptual model to address the most common high distress situations (e.g., relationship distress, veteran or caregiver depression, anxiety, or pain).

Aim 2: Evaluate preliminary effectiveness and feasibility of the CC+C Intervention. A randomized controlled pilot study of distressed dyads will be completed to compare: 1) the established CC intervention, to 2) the CC+C intervention on veteran and caregiver outcomes at 6 months.

Aim 3: Conduct exploratory analyses of the CC+C intervention on veteran long-term care placement at 6 and 12 months and examine two key treatment moderators

(behavioral symptoms and spousal relationship status) that may impact intervention engagement and response to treatment.

Hypotheses for Aims 2 and 3:

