Participants assigned to both groups will have: 1) reduced unmet needs, 2) reduced depressive symptoms, and 3) higher levels of satisfaction with care at 6 months than their baseline assessment values.

Caregivers assigned to CC+C will have greater reductions in caregiver burden at 6 months than those assigned to CC alone. Indicators of relationship strain (e.g., marital distress and/or mutuality) will show greater improvement in CC+C than CC at 6 months. 6 month gains in shared pleasant events, social engagement, and quality of life will also be greater in CC+C than in CC alone. 6-month desire to institutionalize will be lower in the CC+C group than those randomized to CC. Treatment engagement (e.g. action plan completion, attendance) is also predicted to be higher in the CC+C group than in CC.

For Aim 3, we anticipate that individuals who receive the CC+C intervention will have lower rates of placement in long-term care facilities at 6 and 12 months than those who receive CC alone. We also expect that behavioral problems will impact treatment outcomes such that those dyads with higher levels of behavioral disturbance at baseline will have greater change scores at 6 months. Spousal relationship to the veteran is also expected to moderate treatment outcome such that spousal caregivers are anticipated to have lower change scores compared to non-spousal caregivers across time; however, we expect this effect to be attenuated in the CC+C condition.

7. Background, including results of relevant research, gaps in the current knowledge.

Scope of the Problem

Over five million Americans are diagnosed with Alzheimer's disease or a related disorder (ADRD) and rates are expected to triple by 2050¹. It is the 6th leading cause of death in the United States and one in three older adults will have dementia when they die².

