Veterans have high rates of known risk factors that place them at increased risk of developing dementia including: PTSD,³ diabetes^{4,5}, substance use disorders,⁶ and cardiovascular disorders.⁷ Over 7% of veterans 65 and over receiving care through the Veteran's Health Administration (VHA) are currently diagnosed with dementia.⁸ In a study of dementia prevalence among VHA system users, [name], [name], and colleagues found that diagnosis by VISN varied between 5.8% to 9.4%.⁸ VISN 7, where the current work is proposed, had the highest dementia rates of any VISN in the country and was in the region with the greatest rates overall (i.e., the southeast) perhaps reflecting differences by race,⁹ educational achievement,¹⁰ rurality,¹¹ and/or cardiovascular morbidities.

Spouses comprise the largest group of caregivers for individuals with ADRD. This is particularly true for veterans with dementia, most of whom are men cared for by their

wives.¹² Decades of research suggests that spousal caregivers are uniquely vulnerable due to increased isolation, older age, and cohabitation status which reduce opportunities for respite.¹³ Couples in which one individual is diagnosed with dementia often experience substantial depression and frustration adjusting to functional changes and losses in roles, relationship, and independence of the declining loved one.¹⁴⁻¹⁶ Changes in shared intimacy, emotional support, companionship, and reciprocity are consequences of memory loss¹⁷ and associated cognitive changes resulting in grief reactions in up to 71% of caregivers.¹⁸ Some research has cited loss of the relationship with the person as the most distressing element of the disease for caregivers and directly predictive of depression above other aspects of the caregiving context.^{14,17} The unique functional and behavioral impairments associated with ADRD contribute substantially to psychological and physical morbidity of family caregivers and high rates of nursing home placement, with 60% of ADRD caregivers rating the emotional stress of caregiving as “high or very high,” and over one third reporting depressive symptoms.

Gaps in Current Knowledge

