10. Number of the subjects that will be recruited for study

At least seventy dyads (i.e. 70 veterans and 70 caregivers) will be recruited to achieve a final sample. However, caregivers can participate independently if the veteran is too impaired to participate meaningfully in the study.

11. Subject inclusion/selection criteria

Veterans:

- a. Must be age 19 or older
- b. Must have a diagnosis of dementia or a related disorder
- c. Must live in the community (i.e. not in a VA Community Living Center, nursing home, or other facility)
- d. Must cohabitatem with a caregiver;
- e. Must have reliable access to a telephone
- f. Must be willing to consent to participate or provide assent in conjunction with proxy consent if their decision-making capacity is compromised.

Caregivers:

- a. Must be age 19 or older
- b. Must self-identify as assisting with care for at least 8 hours/week
- c. Must be willing to consent to participate.

The study will include women and minorities and aim to represent the percentage reflected in Tuscaloosa VAMC medical care system (12% women, 44% minorities, and 1% Hispanic origin; though numbers of minorities might be slightly lower in the older cohorts targeted for this study as indicated above). No specific inclusion/exclusion criteria related to race/ethnicity are required.

12. Subject exclusion criteria

In addition to meeting the inclusion criteria outlined above, participants will be excluded in the following cases.

Veterans:

- a. Currently incarcerated
- b. Currently pregnant
- c. Dyads experiencing low levels of distress (as defined by a score of 0 or 1 on the Dementia Services Mini-Screen³², see below)

Note. Baseline or post-assessment interviews will be discontinued for Veterans experiencing severe cognitive impairment that would impair their ability to communicate during an interview, consistent with good clinical practices. However, they will not be excluded from participating in intervention sessions as appropriate and their available data (self-report or proxy report) will be retained for analyses.

Caregivers:

- a. Currently incarcerated
- b. Currently pregnant
- c. Experiencing severe cognitive impairment that would impair their ability to communicate during an interview
- d. Dyads experiencing low levels of distress (as defined by a score of 0 or 1 on the Dementia Services Mini-Screen³², see below)

13. Subject exit criteria

- a. Subjects will exit the study once one of the following conditions are met:

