r. The 6-item **Desire to Institutionalize (DTI)** Scale⁵¹, which assesses the caregivers planning, thoughts, and actions about long-term care (LTC) placement over the past 6 months will be used to assess intentions to institutionalize their loved one. Six yes/no items (e.g., taken steps toward placement) are summed for a score of 0-6. Long-term care placement and/or hospitalization of the veteran (institutionalization) will be assessed using a single item rated either by the caregiver or via electronic health record review if the dyad is no longer enrolled in the study (e.g., due to attrition).

s. The 21-item **Care Consultation Satisfaction Survey** will be used to measure the participants' satisfaction with the Care Consultant and the Care Consultation services provided.

Once baseline data are collected, dyads will be randomly assigned to a condition (see interventions delivered below).

Randomization

Blocked randomization stratified by race and gender will be used to assign participants to either the: (a) CC group, or the (b) CC+C group. This two-group experimental design was chosen over other approaches (e.g., no comparison group designs, three-group design, cross-over design, etc.) because it most closely approximates the next level of clinical research (e.g., an efficacy study), which allows for the most directly applicable conclusions.

Interventions Delivered

1. Care Consultation (CC): is an established telephone-based, empowerment intervention that uses coaching and emotional support to mobilize family caregivers and individuals with dementia through psychoeducation, resource referral, psychosocial support, and encouragement of informal and formal service use utilization. A computerized clinical tool utilizing a password-protected VA-hosted website (i.e., operated within the VA server system) called the Care Consultation Information System (CCIS) guides the care consultant through a standardized delivery of protocol components, replacing a paper-based clinicians manual. Rather than a strong focus on assessment, this intervention is designed to quickly identify areas of unmet need through brief trigger questions called the “initial assessment” – much like an interview guide – which then immediately shapes development of concrete action plans.

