Missing values are unavoidable in applied clinical intervention research. Where possible, variables to index the number and reasons for missing values will be documented. Based on the distribution of these missing value indices we may choose to eliminate some participants from the analyses ("list-wise deletion"). The extent that missing values are related to the independent (treatment group) or outcome variables will be assessed and if necessary controlled for statistically. Individuals who complete at least four sessions of the intervention (CC or CC+C) will be included in final analyses when time 2 data are available. Strict intention-to-treat methodologies are too conservative for this relatively small initial pilot study.

Data Analysis:

A series of one-way between subjects analyses of covariance (ANCOVAs) will be used to examine the main effect of “group” on 6 month variables of interest while controlling for values at baseline. The dependent variable in these analyses will be change scores with pre-treatment scores as the covariate. This analysis is statistically equivalent to ANCOVA with pre-treatment scores as the covariate and 6-month scores as the dependent variable, but it has an interpretational advantage in that the change scores represent an individual treatment effect (change during treatment). The change scores also represent the interaction term of a 2 (Group) X 2 (Time) repeated measures ANOVA. Consequently, when other covariates are added to the ANCOVAs to address treatment moderation effects, those covariate effects will be directly interpretable as moderator effects. That is, the added terms will assess the effects of the covariates on changes during treatment irrespective of Group (essentially a Time by Covariate interaction). When the interaction (multiplicative product) of covariate and Group is also added as another term in the ANCOVA, that interaction term will supply the moderating effect of the covariate on change during treatment as function of Group (i.e., differential effect of treatment as a function of the covariate).

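### Spousal status, which the plan itself expects to affect change, is missing from the main Group ANCOVAs and is not stratified; adding it as a covariate is a cheap guard against chance imbalance

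*Combined protocol and SAP*

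**What the plan says.** Aim 3 (section 6) names two key moderators: "behavioral symptoms and spousal relationship status) that may impact intervention engagement and response to treatment". The hypotheses give the second one a direction: "Spousal relationship to the veteran is also expected to moderate treatment outcome such that spousal caregivers are anticipated to have lower change scores" than non-spousal caregivers; "however, we expect this effect to be attenuated in the CC+C condition". So the plan predicts an overall effect of spousal status on the analysed quantity (change), as well as an interaction with Group.

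Section 17 (Randomization) states: "Blocked randomization stratified by race and gender will be used to assign participants to either the" CC or the CC+C group. Spousal status is not a factor. It could be known in time, because "Once baseline data are collected, dyads will be randomly assigned to a condition".

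Section 20 (Data Analysis) tests Group on 6-month change with the pre-treatment score as the covariate. Further variables appear "when other covariates are added to the ANCOVAs to address treatment moderation effects", first alone and then with their product with Group. The nursing home placement model allows for relevant covariates but does not name them. Section 20 also limits the final analyses to those with at least four sessions and available 6-month data, and expects 50 completers from at least 70 recruited dyads.

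**The concern.** A variable that the plan expects to drive change is neither balanced at allocation nor adjusted for in the comparison that answers Aim 2. If one arm happens to contain more spouses, part of the observed Group difference will be a difference in the mix of caregivers. With about 25 dyads per arm, such imbalances are not rare. Keeping only those who complete four sessions can add imbalance after randomisation, which no stratification would prevent.

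The threshold for interpretation makes this matter. Section 20 uses effect size as the main indicator and treats a partial eta squared of 0.01 or more between groups as potentially clinically meaningful. A modest shift can move a result across so low a line in either direction.

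**Working it through.** **The plan's own figure.** There is none on this point. The power calculation is in grant text outside the documents. The step from 70 to 50 implies a loss of 1 − 50/70 = 28.6%.

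**Inputs from the documents.** 70 dyads recruited and 50 completers (section 20); threshold of partial eta squared 0.01 (section 20); spouses expected to change less, attenuated in CC+C (section 6).

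**Assumptions, none of them in the documents.** Equal arms; non-spouse share p of 10–50%, with 20% as the working case; spouse effect b on change of 0.3–0.8 residual SD, with 0.5 as the working case.

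**Yardsticks.**
- Threshold as a standardised difference: d = 2√(0.01/0.99) = 0.20.
- Group standard error with 25 per arm: √(2/25) = 0.28 residual SD.

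**Typical imbalance.** With spousal status left to chance, the SD of the between-arm difference in spousal share is √[4p(1 − p)/(N − 1)]. For p = 0.2 and N = 70 this is √(0.64/69) = 0.096. The typical shift in the Group contrast is b times this: 0.5 × 0.096 = 0.05 SD.

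| Non-spouse share | SD of gap, 35:35 | Shift at b = 0.5 | SD of gap, 25:25 | Shift at b = 0.5 |
|---|---|---|---|---|
| 10% | 0.072 | 0.04 | 0.086 | 0.04 |
| 20% | 0.096 | 0.05 | 0.114 | 0.06 |
| 30% | 0.110 | 0.06 | 0.131 | 0.07 |
| 50% | 0.120 | 0.06 | 0.143 | 0.07 |

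**A less favourable split.** Among 14 non-spouses in 70 dyads, the hypergeometric probability of 10:4 or worse, in either direction, is 0.133. At 10:4 the spousal shares are 25/35 = 71% and 31/35 = 89%, a gap of 6/35 = 0.171. The shift is 0.5 × 0.171 = 0.086 SD.

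**Allowing for attenuation.** If the spouse effect differs by arm, the shift is the mean of the two effects times the gap. With 0.5 SD in CC and, for illustration, 0.25 SD in CC+C, it is 0.375 × 0.171 = 0.064 SD. With no effect in CC+C it is 0.25 × 0.171 = 0.043 SD.

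**What the covariate gains and costs.** The spouse effect explains R² = b²p(1 − p)/[1 + b²p(1 − p)] of the residual variance. With 50 completers the error degrees of freedom fall from 47 to 46, so the net variance ratio is about (1 − R²) × 47/46. At p = 0.2:
- b = 0.3: R² = 0.014, ratio 1.007 (a loss of about 1%).
- b = 0.5: R² = 0.038, ratio 0.982 (a gain of about 2%).
- b = 0.8: R² = 0.093, ratio 0.927 (a gain of about 7%). At p = 0.3, R² = 0.118 and the ratio is 0.901 (a gain of about 10%).

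Break-even is R² = 1 − 46/47 = 0.021, which at p = 0.2 means a spouse effect of about 0.37 SD.

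**The case against.** The strongest reply is that the effect is small and not systematic. Randomisation leaves the Group contrast unbiased over repeated allocation, and the ordinary standard error already reflects chance imbalance. The typical 0.05 SD shift is about a sixth of the Group standard error (0.05/0.28), and even the 10:4 case is under a third (0.086/0.283 = 0.30). Aim 3 is exploratory, this is a pilot, and spousal status does enter the moderation models. All of this stands and limits the point to a modest improvement. It does not explain why a predictor that the plan itself names, and must record for Aim 3, is left out of the main comparison.

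A reader might go further and infer that stratifying by gender is wasted because gender hardly varies. The documents do not support this. The figure "12% women, 44% minorities, and 1% Hispanic origin" describes the medical centre's care system, which recruitment aims to reflect. On that figure veteran gender would be skewed (12% of 70 is 8.4 women) but not constant. Section 17 does not say whose gender is used, and no figure is given for caregiver gender, which could itself be related to spousal status.

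A reader might also infer that non-spouses will be few. Section 7 says "Spouses comprise the largest group of caregivers for individuals with ADRD" and describes most veterans with dementia as men cared for by wives, but it gives no share for this trial. The rule that the veteran must live with a caregiver does not make that caregiver a spouse.

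**Conclusion.** The point holds as a low-cost improvement. The plan predicts that spousal status affects change, yet neither balances it nor adjusts for it in the main Group ANCOVAs. The consequence is exposure to chance imbalance and usually a little lost precision. It is not systematic bias, and spousal status is not absent from the plan.

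In the working case the shift is typically about 0.05 SD. It reaches about 0.09 SD or more with 13% probability, or about 0.04–0.06 SD at the same 10:4 split if the effect is absent or halved in CC+C. That is small beside the standard error of 0.28, but not negligible beside a threshold of d = 0.20. These sizes rest on the assumed non-spouse share, spouse effect and equal allocation. Nothing here shows that race and gender are the wrong stratification factors.

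**What to change.** In section 20, prespecify spousal/non-spousal status as a covariate, beside the baseline score, in the main Group ANCOVAs for every outcome measured in both kinds of dyad. Keep its product with Group for the Aim 3 moderation models. Exclude the Dyadic Adjustment Scale: section 17 uses it in spousal dyads only, so the covariate would be constant.

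Baseline RMBPC may be added in the same way, since section 6 also expects baseline behavioural disturbance to relate to change. Leave it out where it is already the outcome's own baseline score.

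The cost is one sentence in the analysis plan and one error degree of freedom per covariate (47 to 46 for spousal status). If the spouse effect is as small as 0.3 SD, there is a net loss of about 1% in variance. The adjustment needs no new data collection, can be adopted whatever the state of enrolment provided it is fixed before outcomes are compared by arm, and also handles imbalance that arises from the four-session restriction.

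Stratifying dyads not yet enrolled by spousal status is an option only. It needs a new allocation list, gives up balance on gender if it replaces that factor, and does not guarantee balance among those finally analysed.

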Outcome measures for caregivers will be run in separate analyses from those of the veterans with dementia, such that a series of ANCOVAs are anticipated for 1) self-report measures for the caregiver; 2) self-report measures for the veteran with dementia; and 3) proxy-reported measures for the veteran with dementia (as rated by their caregiver). Partial eta squared statistics of effect will be used as the primary indicator of likely treatment effects in this small sample. A large effect is indicated by a partial eta squared (hp^2) greater than or equal to 0.14, a medium effect is determined by a value greater than or equal to 0.06, and small effects are determined by values greater than or equal to 0.01. For the purposes of the current study, between groups effect sizes greater than or equal to .01 (a small effect) will be interpreted as potentially clinically meaningful in the interpretation of results since two active treatments are being compared. Cohen's d statistics will also be calculated for the purposes of the current feasibility study because they are one of the most common methods of estimating effect sizes and are more easily interpreted than the partial eta squared effects. In order to calculate Cohen's d statistics, standard error terms will be converted into standard deviations and used with the estimated marginal means from the post-treatment ANCOVAs. Both types of effect sizes will be calculated. Finally, logistic regression analyses will be conducted to determine if NH placement at 6 and 12 months is differentially related to treatment condition (i.e., group assignment) for individuals with dementia. NH placement (or not) will be the dependent variable in these analyses, and independent variables will include Group and relevant covariates.

21. Risks (physical, psychological, social, and economic) and steps taken to minimize these risks.

Physical Risks: There are no anticipated physical risks with this study. All activities in the study will be within the normal limits of participants' everyday physical demands. Increased veteran activity and/or range of motion could potentially result in exacerbation

of pre-existing pain conditions (e.g., arthritis, etc.); however, potential benefits in strength/decreased disability exceed potential risks.

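### Race and gender stratify the randomisation but are not covariates in the 6-month ANCOVAs; if they are prognostic, the reported standard errors are modestly conservative

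*Combined protocol and SAP*

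**What the plan says.** Section 17 (Randomization) describes the allocation of dyads to CC or CC+C: "Blocked randomization stratified by race and gender will be used to assign participants". It gives no block size or allocation ratio, and does not say whether the race and gender are the veteran's or the caregiver's. Section 17 (Measures, Demographics) collects both variables for both members of the dyad.

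Section 20 (Data Analysis) defines the main analysis as ANCOVAs of the group effect on "6 month variables of interest while controlling for values at baseline". It continues: "The dependent variable in these analyses will be change scores with pre-treatment scores as the covariate". Other covariates are mentioned in three places, none of which brings in the stratification factors:

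- They enter the ANCOVAs "when other covariates are added to the ANCOVAs to address treatment moderation effects". The two moderators named in Section 6 (Aim 3) are behavioural symptoms and being a spouse.
- Under Treatment of Missing Values, statistical control is foreseen where missingness is related to treatment group or outcome.
- The logistic regression for nursing home placement has an unspecified set of covariates.

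On reporting, Section 20 says: "Partial eta squared statistics of effect will be used as the primary indicator of likely treatment effects in this small sample". It treats 0.01 or more as potentially clinically meaningful. Cohen's d is to be built from the ANCOVA adjusted means, with an SD derived from the standard error.

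**The concern.** Stratified allocation largely removes chance imbalance in race and gender from the group comparison. If these factors predict change, the true sampling variation of the group difference falls. A model without them still counts their contribution as residual variance, so its standard error describes a less precise design than the one used. With about 50 completers, even a modest loss deserves attention. Partial eta squared and Cohen's d both inherit the residual error term, so the plan's two effect indices depend on whether the factors are in the model. Leaving the choice open also allows the factors to be added later, outcome by outcome, across a long series of caregiver, veteran and proxy analyses.

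**Working it through.** **Figures in the plan.** Section 20 gives 70 dyads recruited and 50 completers, an implied loss of 20/70 = 28.6%. It states no standard error, alpha, power or expected partial eta squared (the power basis is left to the grant text), so there is no planned precision to reproduce.

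**Inputs.** From the documents: 70 randomised, 50 analysed, 12% women and 44% minorities (Section 11, the medical centre's care population). Assumed: 1:1 allocation, blocks of 4, race in two levels, losses at random, and R² = share of residual variance explained by race and gender after the baseline score, from 0 to 0.20.

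**Step 1: standard error by hand.** If strata were perfectly balanced at randomisation and 50 of 70 remained at random, 20/70 of the imbalance variance would return. Relative to the residual variance, the true variance is (1 − R²) + R² × 20/70 = 1 − R² × 50/70. The reported standard error is too wide by the factor 1/√(1 − R² × 50/70), and a nominal two-sided 5% test has true level 2Φ(−1.96 × factor).

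- R² = 0.05: 1/√0.964 = 1.018; level 4.6%
- R² = 0.10: 1/√0.929 = 1.038; level 4.2%
- R² = 0.20: 1/√0.857 = 1.080; level 3.4%

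Incomplete blocks make the balance less than perfect, so these factors are close to a ceiling.

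**Step 2: simulation** (6,000 runs per row, no true effect, random 50 of 70 analysed).

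| R² | Mean reported SE | True SD of estimate | Excess | Level, baseline only | Level, adjusted |
|---|---|---|---|---|---|
| 0 | 0.2471 | 0.2494 | none | 5.2% | 5.1% |
| 0.05 | 0.2472 | 0.2460 | 0.5% | 5.0% | 5.2% |
| 0.10 | 0.2475 | 0.2413 | 2.6% | 4.3% | 5.0% |
| 0.20 | 0.2469 | 0.2322 | 6.3% | 3.8% | 5.0% |

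Repeat simulations on a different outcome scale gave 0.286/0.280 and 0.286/0.275 at R² = 0.10 (2% and 4%), and 0.287/0.268 at R² = 0.20 (7%), with levels down to 3.3%. An empirical SD from 6,000 runs has a relative error of about 1/√12,000 = 0.9%, which accounts for much of the spread. If all 50 randomised dyads were analysed, the excess would be larger: 0.2472/0.2368 (4%) and 0.2468/0.2281 (8%).

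**Step 3: partial eta squared.** For the same raw difference and ignoring the degrees of freedom, a value e becomes k/(1 + k) after adjustment, with k = [e/(1 − e)]/(1 − R²).

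- R² = 0.10: 0.010 → 0.0111; 0.060 → 0.066
- R² = 0.20: 0.010 → 0.0125; 0.060 → 0.074

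**Step 4: the 0.01 rule.** Under no effect, partial eta squared follows Beta(1/2, df/2). With 47 error degrees of freedom (baseline only) its mean is 1/48 = 0.021 and it reaches 0.01 in 49% of analyses. With 45 (adjusted) the figures are 1/46 = 0.022 and 50%.

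**Step 5: Cohen's d.** The adjusted residual SD is √(1 − R²) times the baseline-only SD. At R² = 0.20 that is 0.894, so d rises by 1/0.894 − 1 = 11.8% with no larger raw difference.

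**Step 6: stratum sizes.** Women among 50 completers: 0.12 × 50 = 6. If race and gender are independent, the two female strata hold 50 × 0.12 × 0.44 = 2.6 and 50 × 0.12 × 0.56 = 3.4 dyads.

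**The case against.** The strongest reply is that everything depends on R², and the documents give no evidence on it. The Background links race to regional dementia prevalence, not to change in burden, mutuality or depression. If R² is near zero, adjustment gains nothing and costs two degrees of freedom. This stands, so the consequence can only be stated conditionally. It is also true that any error is on the conservative side, in a pilot that leads with effect sizes and states no significance level.

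A reader might infer three stronger things that the documents do not support.

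- **That the standard errors are too wide as a matter of fact.** This needs a prognostic strength that is nowhere given.
- **That the plan discards precision worth about 25% more dyads at R² = 0.20.** That figure (1/0.80 = 1.25) compares reported variances. Stratification has already stabilised the unadjusted estimate. The gain in true variance at R² = 0.20 is only about 4% to 9%: for example (0.2281/0.2238)² = 1.04 with all 50 analysed, and (0.2322/0.2235)² = 1.08 with 50 of 70.
- **That real effects will look smaller than they are.** Partial eta squared is lower only in comparison with the adjusted model. Against its population value it is already too high: for a true d of 0.5 (population value about 0.059) the baseline-only mean is 0.075 to 0.077.

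Attrition and the four-session rule weaken the stratum balance among those analysed. That shrinks the overstatement of the standard error, but it also leaves some race and gender imbalance that a baseline-only model does not correct. On balance this favours adjusting.

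**Conclusion.** The mismatch is real: no section commits to race or gender as covariates in a 6-month ANCOVA. Its consequence is conditional and modest. With 50 of 70 dyads analysed and losses at random, the reported standard error is about 2–4% too wide at R² = 0.10 and 6–7% at R² = 0.20. A nominal 5% test then runs at about 4.2–4.4% or 3.3–3.8%. At R² of 0.05 or less nothing material happens. These figures rest on the assumed R², 1:1 allocation and blocks of 4.

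The omission costs efficiency and does not itself bias the group difference. Adjustment does not make the 0.01 threshold informative, since about half of null outcomes cross it under either model. The change is worth making because it aligns the analysis with the design at almost no cost and settles the covariates before the data are seen. It should not be presented as rescuing lost power.

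**What to change.** In Section 20 (Data Analysis), prespecify for every 6-month ANCOVA: change = Group + baseline score + race + gender, with race and gender coded exactly as in the randomisation list. State in Section 17 whether they are the veteran's or the caregiver's. Because the Background describes most of these veterans as men cared for by their wives, the two choices give very different strata.

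Take adjusted means and partial eta squared from this model. State which SD standardises Cohen's d, because the smaller residual SD of the adjusted model raises d without any larger raw difference.

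The cost is one or two sentences and two residual degrees of freedom (47 to 45 with 50 completers), more if race has more than two levels. No new data are needed. With about 6 women among 50 completers if the veteran's gender is used, enter main effects and not the full race-by-gender strata. Expect sparser cells for outcomes restricted to spousal dyads, such as the Dyadic Adjustment Scale.
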